Transthoracic needle aspiration (TTNA) is currently the preferred mode for sampling peripheral pulmonary nodule (PPN) because it has a high diagnostic yield ranging from 80% to 90% [2]. However, it has a 12% to 45% risk of pneumothorax, with 2% to 15% requiring chest tube placement [3]. Flexible bronchoscopy with brushing, washing, and transbronchial biopsy (TBB) is safe but provides a much lower diagnostic yield (14 to 63%) depending on the size and location of PPN [4,5]. A recent meta-analysis including 1033 PPNs revealed that the diagnostic yield of TBB can reach up to 65%, if guidance systems such as electromagnetic navigational bronchoscopy (ENB), virtual bronchoscopy (VB), or radial-probe ultrasound (r-EBUS) are used. However, the negative predictive value (NPV) was reported to be low (0.52) [6,7].

Robotic technology has recently been incorporated into navigational bronchoscopy to improve flexibility, reach, and stability [8,9]. While manual and robot-assisted navigational bronchoscopy technologies have been proven effective in directing the bronchoscopist to achieve proximity to peripheral nodules, further localization with radial ultrasound and/or fluoroscopy is often required to make fine adjustments to align the biopsy needle with the target nodule. Without independent confirmation that a needle is in the lesion, a bronchoscopic lung biopsy that does not show tumor cells is often considered non-diagnostic rather than negative. Needle biopsies may therefore require multiple needle passes, which can cause bleeding. While rarely life-threatening, bleeding can contaminate slides and make a rapid on-site evaluation (ROSE) of biopsy samples challenging. A technology offering independent confirmation that the tip of the needle is within the nodule may reduce the incidence of non-diagnostic biopsies.

Needle-based Confocal laser endomicroscopy (nCLE) is a novel high-resolution imaging technique that uses an excitation laser light to create 'real-time' microscopic images of tissues. nCLE can be integrated into needles allowing real-time cancer detection during endoscopy. In a recent study by Wijmans et al. [10] (ClinicalTrials.gov Identifier: NCT02689050) nCLE of lung tumors and mediastinal nodes was feasible, using an endoscopic ultrasound-guided approach from the esophagus. nCLE malignancy criteria were identified. This study demonstrated that the nCLE technique provides real-time information regarding the malignancy status of lung tumors and mediastinal nodes. Improved needle-based bronchoscopic diagnostics might result in improved diagnostic cancer rate, reduction of surgical diagnostic procedures, reduced costs, and shorter time-from lung nodule detection to final diagnosis allowing treatment at an earlier cancer stage. Ideally, in the future, a target lesion will be identified as being malignant in a real-time fashion and, in the same session, bronchoscopically treated.

The first steps towards real-time optical biopsies were made with EUS-guided nCLE in gastroenterology. Recently, promising data were published on EUS-guided nCLE in lung lesions and mediastinal lymph nodes. Wijmans et al. [10] identified three nCLE characteristics for the detection of malignancy in different subtypes of lung tumors and metastatic lymph nodes (dark enlarged pleomorphic cells; dark cell clusters consisting of overlapping cell structures ('dark clumps'); and the continuous movement of a part of the cells in one direction ('directional streaming')). In this study, nCLE accuracy for detecting malignancy was **90% in tumors** and **89% in metastatic lymph nodes**. Both **inter-observer agreement (k=0.68)** and **intra-observer agreement (k=0.70)** were **substantial**. To our best knowledge, data comparing PPN diagnostic yield of Robotic-nCLE-guided TBNA for lung cancer diagnosis with conventional Robotic-guided TBNA does not exist.

In the present study, we aim to compare the diagnostic yield of Robotic-nCLE-guided TBNA for lung cancer diagnosis to conventional Robotic-guided TBNA using the final diagnosis (histology or follow-up) as the standard reference. Furthermore, we will create an image atlas of the characteristics of nCLE-images in PPNs. Also, we aim to describe tumor types based on in-vivo characteristics. Improved characterization of distal lung lesions might lead to improved and quicker cancer diagnosis and patient care.

Background: nCLE imaging of PPNs under bronchoscopic guidance is feasible and safe.

Primary objective:

To compare the first-pass diagnostic yield of the sequential needle passes (ROSE) between the Robotic-nCLE-guided TBNA arm and the Robotic- guided TBNA arm in PPNs.

Primary endpoint:

Increase of the first-pass diagnostic yield by 20%, from 70% to 90%, between Robotic-nCLE-guided TBNA arm and the Robotic- guided TBNA arm in PPNs.

Secondary objectives:

1. To compare the per-patient diagnostic yield (cumulative pass diagnostic yield: cumulative number of passes until five cumulated passes) of Robotic-nCLE-guided TBNA arm to that of Robotic-guided TBNA arm in PPNs.
2. To compare the proportion of patients with lung cancer treatment in the Robotic-nCLE-guided TBNA arm to that of the Robotic-guided TBNA arm in PPNs.
3. To compare the proportion of patients with follow-up (video-assisted thoracoscopic surgery (VATS) or TTNA or TBNA procedures) in the Robotic-nCLE-guided TBNA arm to that of the Robotic-guided TBNA arm in PPNs.
4. To compare the number of passes needed to obtain a final diagnosis of Robotic-nCLE-guided TBNA to that of Robotic-guided TBNA in PPNs.
5. To assess the diagnostic performance (sensitivity, specificity, PPV, NPV, accuracy) of the sequential cumulative nCLE passes and the sequential cumulative ROSE passes using the final diagnosis as a reference.
6. Feasibility: obtain adequate CLE video footage in >80% of the PPN punctures.
7. To assess the safety of nCLE imaging, as defined by:
 - a. The number and frequency of all AE/SAE from the start of the procedure until end of 12-month follow-up;
 - b. The number and frequency of nCLE procedure-related AE/SAE from the start of the procedure until end of 12-month follow-up.
8. To assess the reproducibility of nCLE criteria with regard to the reference standard. Three nCLE characteristics for the detection of malignancy were identified during Wijmans et al. study [10]:
 - a. Dark enlarged pleomorphic cells;
 - b. Dark cell clusters consist of overlapping cell structures ('dark clumps') and
 - c. Continuous movement of the cells in one direction ('directional streaming').
9. To create an nCLE image atlas for malignant characteristics in PPNs.

Study design: Randomized, controlled, interventional, comparative prospective multi-center study. A maximum of 118 patients with (suspected) PPN will be enrolled (59 in each arm, Robotic-guided TBNA versus the Robotic-nCLE-guided TBNA). All of the enrolled patients will have an indication for tissue sampling in a PPN based on standard (PET-) CT imaging.

Study population:

To be eligible to participate in this study, a study subject must meet all of the following criteria:

- ≥ 21 years of age
- Suspected PPN
- Nodule size in CT between 8 mm and 30 mm (largest dimension)

- Ability to understand and willingness to sign a written informed consent and HIPAA consent document

Subjects meeting at least one of the following criteria will be excluded from the study

- Inability or non-willingness to provide informed consent
- Failure to comply with the study protocol
- Patients with known allergy for fluorescein or risk factors for an allergic reaction
- Use of beta-blocker within 24 hours before the start of the bronchoscopic procedure
- Possibly pregnant, pregnant or breastfeeding women
- Patients with hemodynamic instability
- Patients with refractory hypoxemia
- Patients with a therapeutic anticoagulant that cannot be held for an appropriate interval before the procedure
- Patients who are unable to tolerate general anesthesia according to the anesthesiologist
- Patient undergoing chemotherapy

Intervention: In patients scheduled for a standard bronchoscopic procedure (Robotic-guided TBNA) with cytological aspirations of the PPN, we will perform nCLE imaging during the bronchoscopy just before cytology.

Nature and extent of the burden and risks associated with participation, benefit, and group relatedness

A participating patient might not benefit from participating in this study. However, future patients might benefit from improved lung cancer diagnostics based on these study findings. nCLE combined with EUS has proven to be safe in the field of gastroenterology, lung tumors, and analysis of intrathoracic lymph nodes [10–12]. This minimally invasive imaging technique provides real-time information at a microscopic level about tissues before aspiration. There is little burden related to study participation: before the beginning of the bronchoscopic procedure, fluorescein will be administered intravenously through the existing venous entrance necessary for the sedation. Fluorescein is a standard used dye in hospitals. Adverse reactions are rare (1.1%) and mild in character [13]. According to the literature, in patients without a known allergy to fluorescein, beta-blocker use, or pregnancy, the use of fluorescein is safe. In 2010, Wallace et al. [14] published a retrospective study of all confocal laser endomicroscopy procedures performed between January 2003 and November 2008, or 2,272 procedures (performed under protocol only), and no serious adverse events related to fluorescein injection were identified.

nCLE acquisitions will be performed during Robotic bronchoscopic workup followed by conventional cytological aspirations (routine workup), without aspirations or biopsies for research purposes. The estimated prolonged endoscopy time due to study participation is a maximum of 10 minutes. The patient will not be aware of this as the procedure will be performed under midazolam (fentanyl) or Propofol sedation (following standard practice). Based on previous studies, adverse events are not expected; FNA combined with nCLE is reported to be safe, easy to perform, and a little time-consuming, without adverse events [10,11,15–17]. In conclusion, we believe that the burden and risks associated with study participation are low.

PROTOCOL SIGNATURE PAGE

Needle based confocal laser endomicroscopy for lung cancer diagnosis: A Randomized Controlled Trial

Protocol No.

REVISION 01

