2. First-two-passes cumulative diagnostic yield is calculated as the proportion of patients for which first-two-passes cumulative TBNA pass during the bronchoscopic procedure yielded a definitive diagnosis out of the total number of patients that have received a diagnostic procedure.
3. First-three-passes cumulative diagnostic yield is calculated as the proportion of patients for which first-three-passes cumulative TBNA pass during the bronchoscopic procedure yielded a definitive diagnosis out of the total number of patients that have received a diagnostic procedure.
4. Etc.... until the fifth pass.

The number of patients has been calculated to demonstrate an increase of the TBNA first-pass diagnostic yield by 20%, from 70% to 90%, between the Robotic-guided TBNA and the Robotic-nCLE-guided TBNA, with a statistical power of 80% with a 2-sided significance level of 0.05. A group size of 59 patients per arm has been derived. By including 59 patients in each arm, we expect to image at least 29 malignant nodules (prevalence of 0.5) in each arm.

The study will enroll 118 consecutive patients randomly assigned 1:1 to Robotic-guided TBNA arm or Robotic-nCLE-guided TBNA arm.

5. Treatment of Subjects

Investigational product/treatment

In recent years, confocal laser endomicroscopy (CLE) has emerged as a novel technique that enables *in vivo* microscopic analysis during ongoing endoscopy [24]. CLE is based on tissue illumination with a low-power laser with subsequent detection of the fluorescence light reflected from the tissue. It is a contrast-based technique, the most widely used agent being the intravenously administered fluorescein. The probe of the endomicroscopy system consists of a flexible catheter probe representing a bundle of optical fibers linked to a micro-objective, a laser scanning unit, and the control and acquisition software (Cellvizio® I.V.E system, Mauna Kea Technologies, France). The principle of the technique is based on a laser beam of the defined wavelength being focused towards the targeted tissue, and the recaptured signal is displayed as 'optical biopsies' in a single horizontal plane.

[figure not shown]

Figure 1: A- Locking of the CLE probe to the aspiration needle. B- CLE probe inside endosonography needle. C- Endosonography images of n-CLE measurements (white arrow) inside a lymph node (LN) (Wijmans/Annema et al. [10]).

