- Twelve months follow-up data: repeat diagnostic procedures or new diagnoses on any lung nodule evaluated during the initial bronchoscopic index procedure, as well as healthcare utilization since the bronchoscopic index procedure (including healthcare visits, repeat bronchoscopic procedures, transthoracic biopsy, bronchoscopy, chemotherapy, brachytherapy, radiation therapy, surgical resection, and lymph node dissection).

nCLE image quality:

nCLE image quality for each nodule will be rated by the interventional pulmonologist as:

- **Very poor:** impossibility to observe any structure or criteria
- **Poor:** The observed criteria and structures are hardly recognisable and interpretable
- **Moderate:** Structures and criteria are recognisable and interpretable with close attention, but confidence in the interpretation remains low (may require replaying the sequence frame by frame)
- **Good:** Image quality is sufficient to enable an easy structures and criteria observation and interpretation (may require replaying the sequence frame by frame)
- **Very good:** criteria and structures are recognisable and interpretable very easily

Diagnostic and Therapeutic Management

Lung cancer treatment options are the following:

- **Minimally invasive surgery.** Thoracic surgeons can use minimally invasive techniques when possible, including [video-assisted thoracoscopic surgery \(VATS\)](#) and [robotic surgery](#). Surgeons remove the smallest amount of lung tissue necessary through wedge resection, sleeve lobectomy, and bilobectomy.
- **Highly targeted radiation therapy.** Radiation oncologists have access to the latest technology to carefully shape and precisely deliver radiation to the target. Targeted treatment is available through [intensity-modulated radiation therapy \(IMRT\)](#), volumetric modulated arc therapy (VMAT), [image-guided radiation therapy \(IGRT\)](#), and [proton therapy](#). These techniques reduce the risk of side effects and improve outcomes.
- **Carefully selected systemic therapy.** Mayo Clinic oncologists have access to various systemic treatments, including [chemotherapy](#), targeted therapy, and immunotherapy. Systemic treatments are selected using many factors, including the genetic makeup of your cancer cells.

[figure not shown]

Figure 3: Randomized controlled study device with two arms: Robotic-guided TBNA and Robotic-nCLE-guided TBNA with the different steps

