The tumor board will determine intermediate diagnosis and management recommendations for each patient at the intermediate and final diagnosis phases (see Figure 3). Three therapeutic management options will be considered: "neither treatment nor follow-up", "follow-up", or "treatment" (see above). If the diagnosis is certain, "neither surgery nor surveillance" will be recommended for benign nodules; treatment will be recommended for malignant lesions; either treatment or follow-up will be recommended for indeterminate nodules.

An intermediate diagnosis and an intermediate management recommendation will be provided after the tumor board receives TBNA histological results and recorded in the Case Report Form for each patient of both arms.

A final diagnosis and a final management recommendation will be provided just after the final diagnosis results are received by the tumor board and recorded in the Case Report Form for each patient of both arms.

These intermediate diagnosis and management recommendations will also be compared to the definitive diagnosis and final patient management decisions.

7. Statistical Analysis

Population demographics comparison in both arms:

Statistical analysis will be performed to compare the patient population in terms of demographics to assess whether there are any differences between the populations of the two arms in terms of age, sex, race, type of lung cancers, and cancer prevalence.

Lesion characteristics comparison in both arms:

Statistical analysis will be performed to compare the lesion characteristics to assess whether there is any difference in lesion characteristics between the two arms, in terms of size, location of the nodule, Presence of bronchus sign on computerized tomography, lung zone, positive PET, associated lymphadenopathy, distance closest to fissure, distance from lesion to pleura, and pre-procedure probability of malignancy.

Navigation Accuracy

Distance between the tip of the locatable guide/nCLE Confocal MiniprobeTM and the targeted lung lesion will be measured for each nodule. The median and standard deviation of the distance will be calculated for both arms. Using a statistical test (Student T-test), they will be compared between arms (Robotic-guided TBNA and Robotic-nCLE-guided TBNA).

Navigation success

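### VATS belongs to 'follow-up' in secondary objective 3 and to 'treatment' in Section 6, so a resection after a TBNA cancer diagnosis can count under both and dilute the objective 3 contrast

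*Combined protocol and SAP*

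**What the plan says.** The secondary objectives are given twice, in Section 1 and again just before Section 3, with the same content on this point. Objective 2 is "To compare the proportion of patients with lung cancer treatment in the Robotic-nCLE-guided TBNA arm" against the control arm. Objective 3 is "To compare the proportion of patients with follow-up (video-assisted thoracoscopic surgery (VATS) or TTNA or TBNA procedures", again compared between arms. It does not restrict VATS to diagnostic use, and it does not say whether the procedure must come before or after a diagnosis.

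Section 6, under Diagnostic and Therapeutic Management, opens a list with "Lung cancer treatment options are the following". Its first entry is minimally invasive surgery: "Thoracic surgeons can use minimally invasive techniques when possible, including" VATS. The same part of Section 6 then sets out the tumor board's options: "Three therapeutic management options will be considered: 'neither treatment nor follow-up', 'follow-up', or 'treatment' (see above"). It adds that "treatment will be recommended for malignant lesions; either treatment or follow-up will be recommended for indeterminate nodules". For benign nodules the corresponding wording speaks of surveillance instead of follow-up. Section 8, under Patient management, repeats the three options.

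The rationale in Section 1 hopes for a "reduction of surgical diagnostic procedures". Objective 3 itself states no expected direction, rate or power.

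**The concern.** The same operation sits in two categories that Section 6 keeps apart, and no rule says where it is counted. Take a patient whose cancer is found at the index TBNA and then resected by VATS. The procedure has succeeded and the patient is treated under objective 2. Under the literal wording of objective 3 the patient is also a follow-up event.

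The effect on the comparison has a predictable direction. A higher yield removes repeat diagnostic procedures, which lowers the objective 3 proportion in the nCLE arm. It also produces more confirmed cancers, and each of those resected by VATS raises the proportion in that arm. If objective 3 is meant to show that better sampling spares patients further diagnostic procedures, the second effect works against it. Two analysts could also derive different endpoints from the same records.

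**Working it through.** **Side by side.** How three kinds of patient are classified:

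| Patient | Objective 3, read literally | Section 6 options |
|---|---|---|
| Cancer diagnosed by TBNA, then VATS resection | follow-up | treatment |
| Not diagnosed, then TTNA or repeat TBNA | follow-up | not stated by procedure |
| Not diagnosed, watched by serial CT | not counted | follow-up (surveillance) |

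The first and third rows disagree, so the word 'follow-up' has two meanings in the plan.

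**The plan's own figure.** Section 4, Sample size calculation, plans for an increase "from 70% to 90%, between the Robotic-guided TBNA and the Robotic-nCLE-guided TBNA, with a statistical power of 80% with a 2-sided significance level of 0.05", and arrives at 59 per arm. With the unpooled two-proportion formula, n = (1.96 + 0.842)² × (0.7×0.3 + 0.9×0.1) / 0.20² = 58.87, so 59. The figure reproduces. It concerns first-pass yield. The documents give no rate or power for objective 3.

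**Illustration for objective 3.** Inputs from the plan: 70% v 90%, prevalence 0.5, 59 per arm. Assumptions not in the plan:
- First-pass yield stands in for whole-procedure yield.
- Yield is the same in malignant and benign nodules.
- Every undiagnosed patient has one further procedure.
- A share v of TBNA-diagnosed cancers goes to VATS, the same in both arms.

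Objective 3 rate = (1 − yield) + v × (proportion malignant and diagnosed):
- Control: 0.30 + 0.5×0.70×v = 0.30 + 0.35v
- nCLE: 0.10 + 0.5×0.90×v = 0.10 + 0.45v
- Control minus nCLE: 0.20 − 0.10v

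Power below is by exact enumeration of the two-sided 5% pooled chi-square test.

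| v | Control | nCLE | Difference | Power |
|---|---|---|---|---|
| 0 | 30% | 10% | 20 points | 80% |
| 0.3 | 40.5% | 23.5% | 17 points | 52% |
| 0.6 | 51% | 37% | 14 points | 34% |
| 1 | 65% | 55% | 10 points | 20% |

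**Range.** Let s be the share of the nCLE arm's extra diagnoses that are malignant. The difference is then 0.20 − 0.20×s×v, so the fraction of the contrast lost is s×v. The table uses s = 0.5. With s = 1, v = 0.5 loses half and v = 1 loses all of it. With s = 0 the 20 points survive, although power is still about 60% at v = 0.5 because both rates move toward the middle of the scale.

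**The case against.** The strongest reply is that objective 3 means diagnostic VATS. It names VATS next to TTNA and TBNA, both sampling procedures. Section 5, under Final Diagnosis or Definitive Diagnosis, describes how cases are followed by surgical tissue biopsy, repeat robotic procedure or CT-guided needle sampling, which closely matches the three items in objective 3. Section 6 would class a resected cancer as treatment. This makes the diagnostic reading plausible, so a reader should not infer that misclassification is settled. It does not remove the conflict: objective 3 states its rule without that limit, and Section 6 governs recommendations without defining objective 3.

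The size of the effect is also open to challenge, and that challenge largely stands. Later procedures depend on cumulative yield, which the plan expects to rise over passes to a plateau but does not quantify. Under an assumed cumulative yield of 80% v 90%, power at 59 per arm is only about 34% even at v = 0. Some undiagnosed patients may have serial CT and no further procedure. The 80% in the first row of the table is therefore not a planned power that is being lost.

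A reader might also infer that a VATS wedge of a nodule that proves benign counts under both objectives. That does not follow, because objective 2 counts lung cancer treatment and such a patient has no lung cancer.

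**Conclusion.** The point holds as a conflict between stated rules. Objective 3 counts any VATS as follow-up, Section 6 lists VATS as treatment, and Section 6 treats the two as separate options. Followed literally, a VATS resection after a TBNA cancer diagnosis counts under both objectives, and the objective 3 contrast is attenuated when the higher-yield arm diagnoses and resects more cancers.

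In the illustration the contrast is 20 − 10v points. More generally the loss runs from none to all of it, depending on v and on the malignant share of the extra diagnoses.

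Two stronger conclusions are tempting. One is that most of the benefit is cancelled. That needs high values of v and s, and the documents give neither; with equal yield in malignant and benign nodules the loss is at most half. The other is that the comparison cannot be read in either direction. The figures contradict this: the nCLE rate is lower in every row of the table, which is attenuation without reversal.

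Objective 3 is secondary, with no stated power or direction. The primary endpoint and the 59 per arm are not affected.

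**What to change.** Reconcile both statements of objective 3 with Section 6 (Diagnostic and Therapeutic Management) and Section 8 (Patient management), before between-arm data are seen:

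1. Define the objective 3 event by purpose: any further procedure (repeat TBNA, TTNA, or surgical or VATS biopsy) done to establish or revise the diagnosis of the index nodule within 12 months. Include re-sampling after an initial benign or indeterminate result. Stopping the count at the first tissue diagnosis would miss repeat sampling after a false-negative benign result, which Section 5 anticipates.
2. Count VATS done after a TBNA diagnosis of malignancy only under objective 2.
3. State one rule for a VATS that both diagnoses and treats.
4. Use a separate word, such as surveillance, for the follow-up option in Sections 6 and 8.

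The cost is an edit to the endpoint wording and one derived variable. Section 6, Follow-up assessment, already collects therapeutic and diagnostic procedures and diagnoses related to lung health. The added work is that each VATS must be classified by purpose and by date relative to the diagnosis. The changes concern counting only and do not alter patient care.
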